7 SUBJECT SELECTION

7.1 *Number of Subjects*

A total of approximately 30 NHV and a minimum of 50 or a maximum of 84 CHB participants (not including potential replacements) may be enrolled in the study.

7.2 *Inclusion Criteria*

Inclusion Criteria for Healthy Volunteer Cohorts

To be eligible for enrollment, subjects must meet all the following inclusion criteria:

1. Male or female, 18 to 55 years of age inclusive, at the time of informed consent
2. Able to provide written informed consent prior to the performance of any study specific procedures
3. Body mass index (BMI) between 19.0 and 35.0 kg/m², inclusive

$$\text{BMI} = \text{weight (kg)} / (\text{height [m]})^2$$

4. A 12-lead ECG at Screening and pre-dose assessment that, in the opinion of the PI, has no abnormalities that compromise participant's safety in this study
5. Participants using two effective methods of contraception (double barrier contraception or hormonal contraception along with a barrier contraceptive, both male and female partners) during the study and for 3 months following the dose of ARO-HBV. Males must not donate sperm for at least 3 months after the last study treatment. Male partners of female subjects and female partners of male subjects must also use contraception, if they are of childbearing potential. Females of childbearing potential must have a negative urine pregnancy test at Screening and on Day 1, pre-dose. Females not of childbearing potential must be post-menopausal (defined as cessation of regular menstrual periods for at least 12 months), confirmed by follicle-stimulating hormone (FSH) level in the post-menopausal range.

- Using twice the normal protection of birth control by using a condom AND one other form of the following (abstinence is acceptable at PI's discretion):
 - Birth control pills (The Pill)
 - Depot or injectable birth control
 - IUD (Intrauterine Device)
 - Birth Control Patch (e.g., Ortho Evra)
 - NuvaRing®
 - Surgical sterilization. i.e., tubal ligation or hysterectomy for women or vasectomy for men or other forms of surgical sterilization

Requirement for contraception can be waived in certain circumstances (i.e. same sex relationships) if approved by PI.

6. Willing and able to comply with all study assessments and adhere to the protocol schedule
7. Have suitable venous access for blood sampling
8. No abnormal finding of clinical relevance at the Screening evaluation
9. AST, ALT and Creatinine levels \leq upper limit of normal at Screening

Inclusion Criteria for CHB Patient Cohorts

To be eligible for enrollment, patients must meet all the following inclusion criteria:

1. Male or female, 18 to 65 years of age, inclusive, at the time of informed consent
2. Able to provide written informed consent prior to the performance of any study specific procedures
3. Body mass index (BMI) between 19.0 and 38.0 kg/m², inclusive. Patients with BMI above or below the cutoff may be enrolled at the discretion of the PI based on risks and co-morbidities.

$$\text{BMI} = \text{weight (kg)} / (\text{height [m]})^2$$

4. A 12-lead ECG at Screening and pre-dose assessment that, in the opinion of the PI, has no abnormalities that compromise participant's safety in this study
5. Participants using two effective methods of contraception (double barrier contraception or hormonal contraception along with a barrier contraceptive, both male and female partners) during the study and for 3 months following the dose of ARO-HBV. Males must not donate sperm for at least 3 months after the last study treatment. Male partners of female patients and female partners of male patients must also use contraception, if they are of childbearing potential. Females of childbearing potential must have a negative urine pregnancy test at Screening and on Day 1, predose. Females not of childbearing potential must be post-menopausal (defined as cessation of regular menstrual periods for at least 12 months), confirmed by follicle-stimulating hormone (FSH) level in the post-menopausal range.

- Using twice the normal protection of birth control by using a condom AND one other form of the following (abstinence is acceptable at PI's discretion):
 - Birth control pills (The Pill)
 - *Cohort 12 Only: Female subjects of childbearing potential who are on a stable treatment regimen with hormonal contraceptives (i.e., same dose and not starting or stopping hormonal contraceptive use) for ≥ 3 months prior to screening should continue the same dose regimen until 12 weeks after EOT. Ethinylestradiol-containing contraceptives are only allowed if the ethinylestradiol content is ≤ 20 μg . For female subjects of childbearing potential who will start a hormonal contraceptive treatment during the study, ethinylestradiol-containing contraceptives are not allowed.*
 - Depot or injectable birth control
 - IUD (Intrauterine Device)
 - Birth Control Patch (e.g., Ortho Evra)
 - NuvaRing®
 - Surgical sterilization. i.e., tubal ligation or hysterectomy for women or vasectomy for men or other forms of surgical sterilization

Requirement for contraception can be waived in certain circumstances (i.e. same sex relationships) if approved by PI.

6. Willing and able to comply with all study assessments and adhere to the protocol schedule
7. Have suitable venous access for blood sampling
8. Have a diagnosis of HBeAg positive or HBeAg negative chronic (> 6 months) HBV infection.
9. HBeAg positive at Screening and experienced to entecavir or tenofovir therapy defined as consistently on any entecavir or tenofovir for at least the most recent 12 months (Cohort 9 only).
10. HBeAg positive at Screening and naïve (has never received) any NUC or Interferon therapy (Cohort 8 only).
11. HBsAg at screening ≥ 5 IU/mL
12. Patients with liver Elastography (i.e. FibroScan®) score ≤ 10.5 at or within 3 months of Screening (for Cohort 12 patients must have FibroScan < 9.0 kPa).
13. No prior use of capsid assembly modulators

7.3 Exclusion Criteria

Exclusion Criteria for Healthy Volunteer Cohorts

A potential subject will be excluded from the study if *any* of the following criteria apply:

1. Female subjects have a positive pregnancy test or are lactating.

2. Acute signs of hepatitis/other infection (e.g., moderate fever, jaundice, nausea, vomiting, abdominal pain) at Screening or at baseline
3. Use within the last 14 days or an anticipated requirement for anticoagulants (aspirin is acceptable), systemic (oral, depot or intravenous) corticosteroids, immunomodulators, or immunosuppressants (other than those used in study treatment regimens)
4. Use of prescription medication within 14 days prior to administration of study treatment that in the opinion of the PI or the Sponsor would interfere with study conduct. Topical products without systemic absorption, statins, hypertensive medications, OTC and prescription pain medication or hormonal contraceptives (females) are acceptable.
5. A history of poorly controlled autoimmune disease or any history of autoimmune hepatitis
6. Human immunodeficiency virus infection, as shown by the presence of anti-HIV antibody (sero-positive)
7. Seropositive for HBV or HCV or a history of delta virus hepatitis
8. Has uncontrolled hypertension defined as blood pressure > 170/100 mmHg at screening confirmed by repeat
9. A history of torsades de pointes, ventricular rhythm disturbances (eg, ventricular tachycardia or fibrillation), pathologic symptomatic bradycardia (heart rate < 45 bpm), 2nd degree or 3rd degree heart block, congenital long QT syndrome, prolonged QT interval due to medications, or new elevation or depression in the part of an ECG immediately following the QRS complex and merging into the T wave (ST segment) or new pathologic inverted T waves, or new pathologic Q waves on ECG that are deemed clinically significant in the opinion of the PI. Subjects with a history of atrial arrhythmias should be discussed with the Sponsor Medical Monitor and CRO Medical Monitor.
10. A family history of congenital long QT syndrome, Brugada syndrome or unexplained sudden cardiac death
11. Is taking medications known to prolong the QTc interval (the length of washout from a medication known to prolong the QTc interval will be determined by the PI depending on the medication's half-life)
12. Symptomatic heart failure (per NYHA guidelines), unstable angina, myocardial infarction, severe cardiovascular disease (ejection fraction < 20%, transient ischemic attack (TIA) or cerebrovascular accident (CVA) within 6 months prior to study entry
13. History of malignancy within the last 5 years except for adequately treated basal cell carcinoma, squamous cell skin cancer, superficial bladder tumors, or in situ cervical cancer. Participants with other curatively treated malignancies who have no evidence of metastatic disease and >2 years disease-free may be entered following approval by the Sponsor Medical Monitor
14. History of major surgery within 3 months of Screening

15. Regular use of alcohol within one month prior to the Screening visit (i.e., more than fourteen units of alcohol per week [1 Unit = 150 mL of wine, 360 mL of beer, or 45 mL of 40% alcohol])
16. Has evidence of severe systemic acute inflammation, sepsis, or hemolysis
17. Recent (within 3 months) use of illicit drugs (such as cocaine, phencyclidine [PCP], MDMA,) or positive test for such drugs of abuse at screening. Subjects who are on prescription medications that cause a positive result on urine drug screen are eligible based on PI discretion. Subjects with a positive urine drug screen for opioids, cannabinoids or benzodiazepines may be eligible based on PI discretion.
18. Use of an investigational agent or device within 30 days prior to dosing or current participation in an investigational study
19. Has any clinically significant history or presence of poorly controlled or decompensated neurological, endocrine, cardiovascular, pulmonary, hematological, immunologic, psychiatric, metabolic, or other uncontrolled systemic disease, that may affect participation in the study
20. Blood donation (500 mL) within 7 days prior to study treatment administration.
21. Any concomitant medical or psychiatric condition or social situation that would make it difficult to comply with protocol requirements or put the participant at additional safety risk
22. Has a history of coagulopathy (including deep vein thrombosis and pulmonary embolism) or stroke within 6 months of baseline, and/or concurrent anticoagulant medication(s).
23. Subjects with any of the following laboratory abnormalities:
 - a. International normalized ratio (INR) $> 1.5 \times \text{ULN}$
 - b. Platelets $< 100,000$ cells per microliter
24. Participants who are unable to return for all scheduled study visits
25. Has any other condition that, in the opinion of the PI, would render the subject unsuitable for enrolment, or could interfere with his/her participation in the study

Note: The PI has the sole right to enroll a subject for the study. The Sponsor may discuss with the PI the suitability of enrolment based upon the subject's medical history or screening results, if it is felt that a subject's safety may be at risk.

Exclusion Criteria for CHB Patient Cohorts

A potential patient will be excluded from the study if *any* of the following criteria apply:

1. Female patients have a positive pregnancy test or are lactating.
2. Acute signs of hepatitis (e.g., combination of moderate fever, jaundice, nausea, vomiting, abdominal pain) within 4 weeks of Screening and/or at baseline

3. Use within the last 14 days or an anticipated requirement for anticoagulants (aspirin and other antiplatelet agents are acceptable), systemic (oral, depot or intravenous) corticosteroids, immunomodulators, or immunosuppressants (other than those used in study treatment regimens)
4. Use of prescription medication within 14 days prior to administration of study treatment that in the opinion of the PI or the Sponsor would interfere with study conduct. Topical products without systemic absorption, statins, hypertensive medications, OTC and prescription pain medication or hormonal contraceptives (females) are acceptable
5. A history of poorly controlled autoimmune disease or any history of autoimmune hepatitis
6. Human immunodeficiency virus infection, as shown by the presence of anti-HIV antibody (sero-positive)
7. Is sero-positive for HCV (defined by positive test for HCV RNA), or a history of delta virus hepatitis
8. A history of torsades de pointes, ventricular rhythm disturbances (eg, ventricular tachycardia or fibrillation), pathologic symptomatic bradycardia (heart rate < 45 bpm), 2nd degree or 3rd degree heart block, congenital long QT syndrome, prolonged QT interval due to medications, or new clinically significant elevation or depression in the part of an ECG immediately following the QRS complex and merging into the T wave (ST segment) or new clinically significant pathologic inverted T waves, or new pathologic Q waves on ECG that is deemed clinically significant in the opinion of the PI. Patients with a history of atrial arrhythmias should be discussed with the Sponsor Medical Monitor and CRO Medical Monitor
9. A family history of congenital long QT syndrome, Brugada syndrome or unexplained sudden cardiac death
10. Symptomatic heart failure (per NYHA guidelines), unstable angina, myocardial infarction, severe cardiovascular disease (ejection fraction < 20%, transient ischemic attack (TIA) or cerebrovascular accident (CVA) within 6 months prior to study entry
11. History of malignancy within the last 5 years except for adequately treated basal cell carcinoma, squamous cell skin cancer, superficial bladder tumors, or in situ cervical cancer. Participants with other curatively treated malignancies who have no evidence of metastatic disease and >1 year disease-free may be entered following approval by the Sponsor Medical Monitor
12. History of major surgery within 3 months of Screening
13. Regular use of alcohol within one month prior to the Screening visit (i.e., more than fourteen units of alcohol per week [1 Unit = 150 mL of wine, 360 mL of beer, or 45 mL of 40% alcohol])
14. Recent (within 3 months) use of illicit drugs (such as cocaine, phencyclidine [PCP], MDMA) or positive test for such drugs of abuse at screening. Subjects who are on prescription medications that cause a positive result on urine drug screen are eligible based on PI discretion. Subjects with a positive urine drug screen for opioids, cannabinoids or benzodiazepines may be eligible based on PI discretion.

15. Use of an investigational agent or device within 30 days prior to dosing or current participation in an investigational study
16. Has any clinically significant history or presence of poorly controlled or decompensated neurological, endocrine, cardiovascular, pulmonary, hematological, immunologic, psychiatric, metabolic, or other uncontrolled systemic disease, that may affect participation in the study
17. Any concomitant medical or psychiatric condition or social situation that would make it difficult to comply with protocol requirements or put the participant at additional safety risk
18. Has a history of coagulopathy (including deep vein thrombosis and pulmonary embolism) or stroke within 6 months of baseline, and/or concurrent anticoagulant medication(s).
19. Patients with any of the following laboratory abnormalities at screening:
 - a. Serum creatinine > 1.5 mg/dL (132.6 µmol/L)
 - b. International normalized ratio (INR) > 1.5 × ULN
 - c. Platelets < 70,000 cells per microliter
 - d. Hepatic transaminases (ALT or AST) > 5X ULN
20. Participants who are unable to return for all scheduled study visits
21. Has any other condition that, in the opinion of the PI, would render the patient unsuitable for enrolment, or could interfere with his/her participation in the study

Note: The PI has the sole right to enroll a patient for the study. The Sponsor may discuss with the PI the suitability of enrolment based upon the patient's medical history or screening results, if it is felt that a patient's safety may be at risk

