HBeAg negative or HBeAg positive CHB patients, aged 18-65 years with BMI between 19.0 and 38.0 kg/m² (Cohorts 1b, 1c, 2b, 3b, 4b, 5b, 6, 7, 8, 9, 10, 11 and 12) will be enrolled. Cohort 8 will enroll HBeAg positive treatment naïve patients (no prior chronic exposure to NUCs or Interferon) and Cohort 9 will enroll HBeAg positive NUC experienced patients (on entecavir or tenofovir for at least 12 months). Cohorts 1b, 1c, 2b, 3b, 4b, 5b, 6, 7, 10, 11 and 12 will enroll either HBeAg positive or negative patients regardless of previous NUC or PEG IFN treatment experience. All patients will be started on entecavir or tenofovir on Day 1. Cohort 12 will start on JNJ-6379 on Day 1 and continue oral 250 mg QD through Day 84. Patients currently on PEG IFN will not be allowed.

Summary of Participant Profile by Cohort and Cohort Size:

- Cohorts 1-5: NHVs, adult males and females, aged 18-55 years
 - 6 NHV subjects per cohort
- Cohorts 1b, 1c, 2b, 3b, 4b, 5b, 6, 7, 10, 11 and 12: Any CHB patient regardless of HBeAg or prior therapy status (as long as other Inclusion and Exclusion criteria are met).
 - Cohorts 1b, 1c, 2b, 3b, 4b and 5b will enroll a minimum of 4 and a maximum of 8 patients per cohort.

- Cohorts 6, 7, 10 and 11 will enroll a maximum of 4 patients per cohort.
- Cohort 12 will enroll 12 patients.
- Cohort 8: HBeAg positive treatment naïve patients (no prior chronic exposure to NUCs or Interferon)
 - Cohort 8: Maximum of 4 patients per cohort
- Cohort 9: HBeAg positive NUC experienced patients (on entecavir or tenofovir for at least 12 months).
 - Cohort 9: Maximum of 4 patients per cohort

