6.2 Rationale for Study Design

This first-in-human study plans to investigate ARO-HBV in adult healthy volunteers (NHVs) and HBV patients to evaluate the drug's safety and tolerability as well as its pharmacokinetics in healthy volunteers and pharmacodynamics in HBV patients, following a single (or multiple subcutaneous doses in HBV patients). The study initiates in NHVs because the single dose risk is considered low. Additionally, this population will be otherwise healthy without co-morbidities that may increase risk

for toxicity. The siRNA triggers in ARO-HBV are targeted against the mRNA transcripts generated by HBV viral cccDNA and integrated DNA. Since NHVs will not have HBV infection the potential for toxicity due to pharmacodynamic (e.g. “on-target”) effect is very low. After a period of post-dose safety evaluation in NHVs at each dose level, multi-dose (3 dose) cohorts in HBV patients at the same dose levels are planned (See Figure 1). Multiple doses of ARO-HBV are employed in the HBV patient cohorts as it is highly likely that prolonged reduction of viral antigens will be required to elicit functional cures. It is also important to note that this study excludes patients with excessive co-morbidities. HBV patients enrolled will not have other co-morbid conditions which could increase their risk of adverse effects to ARO-HBV. The anticipated safety profile in NHVs and HBV patients is likely to be very similar. This is supported by Sponsor’s experience with ARC-521 Injection and ARC-520 Injection, which were siRNA therapeutics studied in single and multi-dose studies in NHV and CHB patient populations. Both ARC-521 Injection and ARC-520 Injection demonstrated a favorable safety profile in NHVs and HBV patients. Variation of dose frequency in the HBV patient cohorts (See Figure 1) is important to understand the dosing regimen that produces the deepest and most rapid reduction in viral antigen.

This study is similar to the ARC5211001 study which was executed successfully at the same site in New Zealand in NHVs and HBV patients.

The study is double-blind to limit the occurrence of conscious and unconscious bias in trial conduct and interpretation. Blinding will be achieved using a PBO product (0.9% normal saline). Inclusion of participants receiving PBO will reduce bias in the assessment of drug safety and tolerability. The study is randomized with a 2:1 (active:PBO) ratio to reduce bias.

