Documentation of the participant's fulfillment of the entry criteria, for all participants considered for the study and subsequently included or excluded, is to be completed by the PI, or medically qualified designee. Documentation of screening failure details will be recorded using eligibility screening forms or a participant screen failure log. Procedures outlined in the Schedule of Assessments will be performed. Meals and water will be provided while participants are confined at the clinical facility. Timing will abide by fasting restrictions outlined in Section 7.5.

9.3.2 *Demographics/Medical History*

Medical History will include medication use over the previous 30 days, including vitamins, over-the-counter, prescription drugs, recreational drugs or supplements and alcohol and tobacco use.

9.3.3 *Physical Exam*

A complete physical exam will be performed at Screening and as per Schedule of Assessments.

At Screening, height (centimetres, without shoes) and weight (kilograms, without shoes) will be obtained to determine BMI.

At all other time points outlined in the Schedule of Assessments, a symptom-directed physical exam will be performed if indicated.

9.3.4 *Electrocardiogram*

A single 12-lead ECG measurement will be obtained at time points outlined in the Schedule of Assessments after the participant is supine for at least 3 minutes. Any abnormal ECGs will be repeated in triplicate, with each measurement approximately 1 minute apart. ECGs will be performed prior to venipuncture and other invasive procedures.

9.3.5 *Vital Sign Assessments*

Systolic/diastolic blood pressure, temperature, heart rate, respiratory rate (breaths/min) will be obtained at time points outlined in the Schedule of Assessments after the participant is seated or semi-supine for at least 3 minutes. Vitals signs will be obtained prior to venipuncture and other invasive procedures.

9.3.6 *Clinical Laboratory Tests & Pharmacodynamic Values*

Blood and urine samples will be collected to perform clinical laboratory tests run at a central laboratory. Participants will be required to fast for the Screening sample collections.

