1	35 mg	200 mg/mL	0.175 mL	Single
2, 2b	100 mg	200 mg/mL	0.5 mL	Single
3, 3b	200 mg	200 mg/mL	1.0 mL	Single
4, 4b	300 mg	200 mg/mL	1.5 mL	Single
5, 5b	400 mg	200 mg/mL	2.0 mL	Two (at separate sites)

**Dose for Cohorts 6, 7, 8, 9, 10 and 11 to be determined based on safety and viral antigen response seen in Cohorts 2b, 3b, 4b, and 5b. The planned dose level for Cohorts 6 through 11 is between 100 and ≤ 400 mg.*

22. **Section/page:** 11.5, Pharmacodynamic Data, pp. 67-68

From:

The whole blood collected for pharmacodynamic analysis following multiple doses of ARO-HBV at different dose levels will undergo analysis for changes in HBV-DNA, HBV-RNA (if scientifically feasible) and viral antigens based on reference laboratory (VIDRL) generated values.

To:

The whole blood collected for pharmacodynamic analysis following multiple doses of ARO-HBV at different dose levels will undergo analysis for changes in HBV-DNA, HBV-RNA (if scientifically feasible) and viral antigens based on reference laboratory (VIDRL) generated values. *Cellular immunologic assessments will also be conducted (if scientifically feasible) at University of Auckland.*

Immunology assessments (CHB patients only)

- *Changes in profile from pre-dose to post-dose time points for: T cell subsets (activation and exhaustion state), NK cell subsets (activation and exhaustion state), B cell subset, monocyte subsets. To be conducted if scientifically feasible.*
- *Changes from pre-dose to post-dose time points for: HBV antigen specific T cell response (including HBcAg, HBsAg). To be conducted if scientifically feasible.*

PROTOCOL AMENDMENT SUMMARY OF CHANGES

PROTOCOL NUMBER: AROHBV1001

STUDY TITLE: A Phase 1/2a Single Dose-Escalating Study to Evaluate the Safety, Tolerability and Pharmacokinetic Effects of ARO-HBV in Normal Adult Volunteers and Multiple Escalating Doses Evaluating Safety, Tolerability and Pharmacodynamic Effects in HBV Patients

VERSION/DATE: Version 3.0, 26 July 2018

OVERVIEW/RATIONALE:

This amendment:

1. Based on previous experience with siRNA compounds targeting HBV (including ARC-520) subjects continued to experience anti-viral effects and in some cases HBsAg becoming undetectable even six months or more after the last dose received. For these reasons, infrequent follow up to measure further changes in viral antigens every 2 months for approximately 1 year after the last planned dose will allow optimal monitoring of patient benefit.

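### The 30-day washout lets a CHB patient previously given an HBV siRNA enter with a Day 1 HBsAg that may still reflect the earlier drug, and no analysis takes account of it

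*Protocol*

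**What the plan says.** Protocol 7.3, CHB criterion 15, excludes "Use of an investigational agent or device within 30 days prior to dosing or current participation in an investigational study". It has two limbs, a 30-day look-back and a bar on being in a study now.

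The other CHB criteria do not mention siRNA, ARC-520, ARC-521, ARO-HBV or entry to a second cohort. Most cohorts are open to "Any CHB patient regardless of HBeAg or prior therapy status (as long as other Inclusion and Exclusion criteria are met" (Protocol 6.1). Cohort 8, the treatment-naïve cohort, requires "HBeAg positive at Screening and naïve (has never received) any NUC or Interferon therapy (Cohort 8 only", so earlier siRNA would not remove that label. One investigational class is excluded outright, by Protocol 7.2 CHB criterion 13: "No prior use of capsid assembly modulators". Criterion 11 sets an entry floor: "HBsAg at screening ≥ 5 IU/mL".

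The Version 3.0 summary of changes explains why CHB patients are followed beyond Day 113. With earlier HBV siRNAs, including ARC-520, "subjects continued to experience anti-viral effects and in some cases HBsAg becoming undetectable even six months or more after the last dose received". That follow-up is still in force (Protocol Table 1.5).

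The SAP takes baseline as the last pre-dose value (section 3). It measures the HBsAg reduction from Day 1 to nadir as the response to ARO-HBV (2.2.2), and defines duration of response by return to within 20% of baseline (section 11).

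**The concern.** The look-back is far shorter than the period over which the sponsor itself expects this drug class to act. A class exclusion was written for capsid modulators but not for the class under test.

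If a previously treated patient enters, Day 1 is not an untreated level. HBsAg may be suppressed and stable, still falling, or rebounding. The secondary activity endpoint, HBsAg loss and duration of response all depend on that level or on what follows it. The CHB cohorts have no control arm and run from 4 to 12 patients, so one such patient can matter. A patient could also contribute to two cohorts. Cohorts 1b and 1c deserve most care: they were added to read dose response at low doses, after the first patients in Cohorts 2b to 5b had been dosed.

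**Working it through.** The documents give no figure on this point to reproduce. The check is day arithmetic, a comparison of provisions, and an illustration of size.

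**Inputs**
- Look-back: 30 days (Protocol 7.3, CHB criterion 15).
- Last ARO-HBV dose: Day 57 for Q28D, Day 29 for Q14D, Day 15 for Q7D (SAP 2.1).
- Completion: Day 113, with re-consent needed for additional follow-up (Protocol 6.4).
- Stated persistence: six months, taken here as 183 days.
- Cohort size: 4 to 8 for Cohorts 1b and 1c (Protocol 6.1).
- Residual effect: 0.5 to 1.5 log. This is an assumption. The only depth given is a maximum of 1.9 log for ARC-520 (Protocol 4.3), which is not a residual.

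**1. Gap from last dose to completion** = completion day minus last dose day. The right-hand column shows the alternative reading in which participation lasts to the 90-day phone call, Day 113 + 90 = Day 203.

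| Regimen | To Day 113 | To Day 203 |
|---|---|---|
| Q28D | 113 − 57 = 56 days | 203 − 57 = 146 days |
| Q14D | 113 − 29 = 84 days | 203 − 29 = 174 days |
| Q7D | 113 − 15 = 98 days | 203 − 15 = 188 days |

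At Day 113 every gap exceeds 30 days and is below 183. On the longer reading, Q28D and Q14D are still below 183.

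**2. Patients in additional follow-up.** They are current participants and so are excluded. Staying to Day 393 gives at least 393 − 57 = 336 days; staying to Day 337 (Cohort 12) gives 337 − 57 = 280 days. Both exceed six months. The route is therefore open only to those who decline or leave follow-up, or who withdraw early.

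**3. Calendar.** The Version 3.0 summary, dated 26 July 2018, describes Cohorts 2b to 5b as already filled. Assuming those patients had been dosed by then, Day 113 fell no later than 26 July + 112 days = 15 November 2018. Version 4.0 added Cohorts 1b and 1c on 1 October 2018. The sequence is feasible.

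**4. Would the analysis respond?** SAP section 4 reviews PD-population membership for patients with protocol violations, but this patient has none. The subgroups in section 11 are baseline HBV DNA, HBeAg status, IL28B genotype, and naïve or NUC-experienced status. None uses prior siRNA exposure.

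**5. Size in one cohort from one patient.** If the nadir is unaffected by the earlier drug and Day 1 is already lowered by r, the mean decline is understated by r/n:
- n=4: 0.5/4 = 0.125 to 1.5/4 = 0.375 log
- n=8: 0.5/8 = 0.0625 to 1.5/8 = 0.1875 log

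If instead HBsAg is still falling at Day 1 and the earlier drug contributes a further fall f, the mean decline is overstated by f/n. The formula is the same with the opposite sign.

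**6. HBsAg loss.** One patient is 1/4 = 25 or 1/8 = 12.5 percentage points. Passing from the 5 IU/mL floor to below 0.05 IU/mL needs a fall of more than log10(5/0.05) = 2.0 log after screening. That exceeds the 1.9 log maximum cited for ARC-520, so a loss caused by the earlier drug alone looks unlikely. The sponsor's remark about late loss stops it from being ruled out.

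**The case against.** Much of the case on the other side stands.

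- **Detection is partly possible.** Quantitative HBsAg is drawn at Screening and on Day 1 in every CHB schedule, and all virology is listed by subject, so a clear pre-dose fall would be visible. SAP 7.1 covers the type of prior treatments, and SAP 10.2 lists prior medications. A reader might infer that the plan is blind to earlier siRNA; it is not. What is missing is a required record of it and any analysis that uses it.
- **History is not confined to 30 days.** Protocol 9.3.2 says "Medical History will include medication use over the previous 30 days", which sets a minimum content. Criteria 9, 10 and 13 need a longer treatment history.
- **The route is narrow.** The bar on current participation removes patients in follow-up, and the HBsAg floor removes the most deeply suppressed. Protocol 8.8 gives each patient one permanent identifier, and nothing provides for re-enrolment, though nothing forbids it.
- **Site overlap has limits.** The ARC-521 study was "executed successfully at the same site in New Zealand in NHVs and HBV patients". That might suggest a route into Cohort 12, but Cohort 12 is open in Hong Kong only. Nor do the documents date the last ARC-520 or ARC-521 doses, so they do not show that anyone was within six months of one.
- **The six-month statement is a rationale.** It concerns earlier siRNAs, and HBsAg becoming undetectable is reported for some cases only. It sets no persistence period for ARO-HBV, so it is in tension with criterion 15 without formally contradicting it.
- **The study is descriptive.** Its primary objective is safety, and the SAP plans no hypothesis tests.

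These points reduce the likelihood and weight of the problem. None of them closes the eligibility gap.

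**Conclusion.** The concern holds as a gap in the entry rule and in the planned analyses. A patient 56 to 98 days past the last ARO-HBV dose can satisfy every CHB criterion as written, while the sponsor's own reasoning allows for continuing effects at that point. Such a patient would stay in the PD population with a compromised baseline.

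The size is conditional. With one such patient and the assumed 0.5 to 1.5 log, a cohort mean moves by about 0.13 to 0.38 log at n=4 or 0.06 to 0.19 log at n=8, in either direction. With no such patient the effect is zero. A reader might infer that the HBsAg results are biased, or always understated. The documents support neither: they do not show that any exposed patient enrolled, and the direction depends on whether HBsAg was suppressed, falling or rebounding at Day 1. Nor is the problem beyond repair, since exposed patients can be identified and set aside. This is an inexpensive improvement to a proof-of-principle study and leaves its primary safety objective untouched.

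**What to change.** 1. **Any further enrolment:** reconcile criterion 15 with the stated persistence of effect by extending Protocol 7.2 CHB criterion 13 to prior HBV-directed siRNA, naming ARO-HBV received in an earlier cohort.
2. **Patients already enrolled:** record lifetime HBV siRNA exposure (product and date of last dose) and any earlier cohort membership, and list both with the baseline disease characteristics in SAP 7.1.
3. **Analysis:** repeat the HBsAg nadir, HBsAg-loss and duration-of-response tables without exposed patients. If there are none, one sentence in the CSR settles the matter.

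The cost is one criterion line, a small addition to the baseline record and one extra set of tables, plus a slightly smaller patient pool if enrolment continues. The SAP reports an interim analysis of Day 113 data for all cohorts with a November 2019 cut-off, so items 2 and 3 probably carry most of the remaining value.
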